4.4. Tertiary/Exploratory Endpoint(s) Analyses

CCI

CONFIDENTIAL

217884

[figure not shown]
CCI

CONFIDENTIAL

217884

CCI

CCI

4.5. Safety Analyses

Refer to Section 4.2.1

4.5.1. Safety Review Team (SRT) & Internal Safety Review Committee (iSRC)

As the investigational study intervention will be administered to humans for the first time, an SRT will be appointed for the study.

For Phase 1, the SRT will receive unblinded summaries of safety data that will be generated by the independent Data Analysis Centre (iDAC) who will have access to the randomization scheme. The unblinded summaries will include all results from the safety analysis by study group. For Phase 2, the SRT and iSRC will respectively receive blinded and unblinded summaries of safety data that will be generated by the iDAC. The blinded summaries will include all results from the safety analysis by age group while the unblinded summaries will include all results from the safety analysis by age and study group.

The safety holding rules for Phase 1 and Phase 2, are defined in [Table 5](#) and [Table 6](#) respectively. If met, holding rules will trigger a hold of the study intervention administration. Holding rules 1a-f will be assessed by the investigator on a continuous basis. Holding rules 2a and 2b will be assessed by the iSRC and/or SRT as applicable

during the safety evaluations of the data. Meeting any of these holding rules will trigger a hold of study intervention administration irrespective of number of participants enrolled and/or timing of the event, for all the study groups.

If a holding rule was met or safety signal observed during the SRT or iSRC meeting, all dose administrations will cease immediately, but all other procedures relating to safety and immunogenicity assessments will continue. Following additional assessment by the SRT or iSRC, a decision to continue, suspend or modify the conduct of the study will be taken by the committee.

In addition to the BLRM analysis (Phase 1 only), the following statistical analyses will be conducted on holding rules in both Phase 1 and 2:

- Tabular listings for all holding rules together will be generated and include information on study group, participant number, holding rule, dose, and details including the severity grade, event outcome etc.
- Detailed listings on any event related to any holding rule will be generated for each holding rule
- Number and percentage of participants meeting each holding rule will be tabulated with exact 95% CI. This analysis will be done by group and after each dose.

Table 5 Study holding rules for Phase 1

Holding rule	Events, per dose and per individual study group	Number of participants to pause dosing in all groups, pending further evaluation by the SRT
1a	Death or any life-threatening SAE regardless of causality	≥1
1b	Any non-life-threatening SAE that cannot reasonably be attributed to a cause other than study intervention administration as per Investigator or Sponsor assessment	≥1
1c	Any withdrawal from the study (by investigator or participant request) due to a Grade 3 AE that cannot reasonably be attributed to a cause other than study intervention administration	≥1
1d	Necrosis at the injection site	≥1
1e	Confirmed myocarditis or pericarditis events not clearly attributable to any cause other than study vaccine	≥1
1f	Laryngospasm, bronchospasm, or anaphylaxis within 24 hours after administration of study intervention	≥1
2a	Maximum number of participants with the same Grade 3 solicited local or systemic AE in an investigational vaccine group, with onset within the 7-day (Day 1-7) post-dosing period	≥2
2b	Maximum number of participants with the same or similar Grade 3 related unsolicited AE in an investigational vaccine group, including events with an identical MedDRA High Level Term and events assessed as clinically similar. Includes any Grade 3 or above laboratory abnormalities* of clinical relevance, symptomatic or not, as determined by the investigator	≥2

* Grading of laboratory parameters will be based on the FDA Guidance for Industry "Toxicity Grading Scale for Healthy Adult and Adolescent Volunteers Enrolled in Preventive Vaccine Clinical Trials". N/A: not applicable

Table 6 Study holding rules for Phase 2

Holding rule	Events, per dose and per individual study group	Number of participants to pause dosing in all groups, pending further evaluation by the iSRC
1a	Death or any life-threatening SAE regardless of causality	≥1
1b	Any non-life-threatening SAE that cannot reasonably be attributed to a cause other than study intervention administration as per Investigator or Sponsor assessment	≥1
1c	Necrosis at the injection site	≥1
1d	Confirmed myocarditis or pericarditis events not clearly attributable to any cause other than study vaccine	≥1
1e	Laryngospasm, bronchospasm, or anaphylaxis within 24 hours after administration of study intervention	≥1
2a	Maximum number of participants with the same Grade 3 solicited local or systemic AE (same solicited AE lasting 2 consecutive days [48 hours] or more as grade 3)* in an investigational vaccine group, with onset within the 7-day (Day 1-7) post-dosing period	≥5% (and ≥2)
2b	Maximum number of participants with the same or similar Grade 3 related unsolicited AE in an investigational vaccine group, including events with an identical MedDRA High Level Term and events assessed as clinically similar.	≥5% (and ≥2)

* E.g., 2 cases of grade 3 fever occurring 2 consecutive days in 2 participants in the same group

The TFLs to be generated to support SRT and iSRC reviews will be detailed in a dedicated output programming specification (OPS).

4.5.2. Internal Data Review Committee (iDRC)

An iDRC will be set up in the study for the purpose of reviewing all available data and recommending the composition of the investigational study intervention formulations to be assessed Phase 2. Statistical interim analyses will be performed to support iDRC data reviews at pre-planned time points (Section 4.7). Refer to Section 4.3 of the protocol for details on selection of doses for further assessment for the next phase of the study.

4.6. Other Analyses

4.6.1. Subgroup Analyses

No subgroup analyses are planned.

4.7. Interim Analyses

In addition to the analyses detailed below, additional analyses, e.g., safety analyses, may be conducted to support the SRT, iSRC and iDRC decisions, as described in Section 8.3.7.1 of the protocol. Refer to Section 10.1.6 of the protocol for the SRT, iSRC and iDRC roles.

As this study is descriptive and each analysis will be completed on expected final immunogenicity data, there will be no type I error adjustment for the different analyses. All interim analyses will be based on the ES.

4.7.1. Sequence of Analyses

Two interim analyses are foreseen and will be conducted upon availability of all primary endpoints up to Day 29 for participants in Phase 1 and Phase 2, respectively. CCI [REDACTED]

[REDACTED] For the observer-blinded Phase 2 interim analyses, a restricted study team will be unblinded to individual participant data and all efforts will be made to ensure the participants, investigators and monitoring staff blinding is maintained up to study end. The rest of the study team will have access to group data but will remain blinded to individual participant data and treatment assignment until the end of the study. It is possible, however, due to the limited sample size, that unblinding occurs for a few participants having a specific AE or SAE (e.g., an AE/SAE occurring only in a single participant). Therefore, anyone having access to the results could become unblinded regarding those few specific cases.

An analysis with all primary and secondary endpoints obtained until the last visit (Day 183) will be performed and made available to the investigators and submitted to regulatory authorities, as appropriate. This may be performed separately for each phase. Analysis of tertiary endpoints may be performed at a later stage. Tertiary analyses deemed futile due to the other study results will not be analyzed nor reported.

4.8. Changes to Protocol Defined Analyses

The BLRM described on Section 4.2.1.5 has been modified to include 2 slope parameters accounting separately for the total amounts of CCI [REDACTED] in each formulation which deviates from that specified in the protocol amendment 1 (Dated: 07 April 2023) where only one slope accounting for the sum of total amounts of both CCI [REDACTED] in each formulation was planned. To focus the laboratory testing, only participants exposed to mRNA vaccines with CCI [REDACTED] in the formulation and control group will be included in the subset for CCI [REDACTED] testing. In CCI [REDACTED]

Section 5.2 is updated to reflect the actual unevaluable rate and lower half-width used for Phase 2 sample size estimation.

5. SAMPLE SIZE DETERMINATION

5.1. Sample Size Determination for Phase 1

The study is designed to provide a reasonable precision for the rate of Grade 3 solicited events and to describe the safety profile of an mRNA-based vaccine. For each investigational study intervention group, it is expected that 24 participants will be enrolled. Assuming a maximum acceptable rate of Grade 3 solicited events of 18%, it is

possible to calculate the probability of a lower true Grade 3 solicited event rate given a different number of participants with Grade 3 solicited event(s). [Table 7](#) provides the estimate and 95% credibility interval for a given observed number of participants for a sample size of 24 participants per study group (assuming a Beta [0.5,0.5] prior distribution). For example, if 4 participants report Grade 3 solicited event(s) among 24 exposed participants, the posterior probability that the true Grade 3 solicited event rate is <18% is 54.5%.

Table 7 Posterior probability estimates of Grade 3 solicited event rate <18%

Number of participants with Grade 3 solicited event(s)	Estimate (95% credibility interval) in %	Probability Grade 3 solicited event rate <18%
0	2 (0 - 9.8)	99.8
1	6 (0.5 - 17.9)	97.6
2	10 (1.8 - 24.1)	89.9
3	14 (3.6 - 29.7)	74.8
4	18 (5.9 - 34.9)	54.5

A further description of the BLRM, including prior, hypothetical data scenarios of number of Grade 3 solicited events that could occur in the actual study, and the decision guides are presented in Section 10.7 of the protocol.

5.2. Sample size determination for Phase 2

The primary objective is to explore how the different formulation(s) or dose level(s) of mRNA-based vaccine compare to licensed control group(s).

The sample size of 108 evaluable participants in each dose level cohort and age group, is expected to provide a 95% CI for group difference in SCR with a lower half-width below 13.3% for difference in seroconversion rates for the different strains ([Table 8](#)) and a 95% CI with an expected half-width of 1.36-fold for the group geometric mean concentration ratio considering a population standard deviation of 0.5 in log10 transformation concentration post-dosing and 10% of unevaluable participants per group.

Table 8 Half-width of 95% CI for the group difference in seroconversion

Control	Strain	Proportion (%)	95% CI of Proportion (%)*	Lower half-width of 95% CI (%)
CCI				

*Obtained from meta-analysis of historical data CCI

CCI

6. SUPPORTING DOCUMENTATION

6.1. Appendix 1: Study Population Analyses

Unless specified otherwise, the study population analyses will be based on the enrolled set.

6.1.1. Screening Failure

A summary of the number and percentage of participants who failed screening will be provided along with the inclusion/exclusion criteria failed. This summary will be based on the screening set.

6.1.2. Participant Disposition

A summary of the number and percentage of participants who completed the study as well as those who prematurely withdrew from the study will be provided. Reasons for withdrawal will be summarized for the enrolled set.

6.1.3. Demographic and Baseline Characteristics

The demographic characteristics including age, sex, ethnicity, height/weight, body mass index (BMI) (kg/m^2) on Day 1, race, country, and flu vaccination status in the past 2 years will be summarized with descriptive statistics. In addition, the following age categories will be summarized: 18-64, 65-84 and ≥ 85 based on the Enrolled Set, ES and PPS.

6.1.4. Protocol Deviations

Important protocol deviations are a subset of protocol deviations (PDs) that may significantly impact the completeness, accuracy, or reliability of the study data or that may significantly affect a participant's rights, safety, or well-being. Important PD rules will be developed and finalized before database lock.

Important PDs include, but are not limited to, the following:

All participant data is excluded from the PPS:

- Study intervention not administered at all
- Invalid/missing informed consent
- Fraudulent data
- Participants got dosed but not as per protocol
- Study intervention storage temperature deviation which is not accepted by quality
- Expired study intervention administered

- Ineligible participant
- Participants randomized using the wrong stratification factor (incorrect age group)

Participant data collected on the day or after the event is excluded from the PPS:

- Influenza disease infection, new malignancy and immunocompromised condition
- Administration of concomitant vaccine(s) forbidden in the protocol
- Administration of any medication forbidden by the protocol, namely administration during the study period of investigational or non-registered product (drug, vaccine or invasive medical device) other than the study intervention, of long-acting immune-modifying drugs or of immunoglobulins and/or any blood products or plasma derivatives with the exception of monoclonal antibodies specifically directed against the spike protein of SARS-CoV-2 virus, for treatment of COVID-19 disease.

Participant lab data collected on the day of the event is excluded from the PPS:

- Participants did not comply with blood sample schedule (see [Table 9](#) and [Table 10](#))
- **CCI** [REDACTED]
- Serological results available but results unreliable (e.g., wrong blood sample management)

The number of participants with important protocol deviations will be summarized by study group across time points and at Day 28 and Day 183. Important protocol deviations will be listed with date of occurrence, deviation description, and analysis set from which participant is excluded. Important protocol deviation summary will be based on the Enrolled Set.

The important PDs will be reported in the Clinical Study Report (CSR). The important PDs leading to elimination from the PPS will be summarized for the ES and the important PDs leading to elimination from the ES will be summarized for the Enrolled Set.

Table 9 Intervals between study visits. Phase 1

Interval*	Planned visit interval	Allowed interval range
Screening Visit** → Visit 1	1-28 days	1 – 28 days
Visit 1 → Contact 1***	1 day	1 day
Visit 1 → Contact 2	2 days	2-3 days
Visit 1 → Visit 2	7 days	6-8 days
Visit 1 → Visit 3	28 days	28-35 days
Visit 1 → Visit 4‡	91 days	84-98 days
Visit 1 → Visit 5‡	182 days	180-210 days

* Interval is computed as the difference between 2 dates

** Screening Visit is planned for participants enrolled in Phase 1 and needs to be performed within 28 days before Visit 1, with sufficient time to receive/review the hematology, biochemistry, HbA1c and urinalysis results. When applicable, a re-screening visit (including blood and urine sample collection, physical examination and re-checking of inclusion/exclusion criteria) may be scheduled at any time (but only once to assess eligibility) before Visit 1. In this case, all screening procedures must be completed within 28 days before Visit 1 (Day 1). Only laboratory results from the re-screening visit, if it occurs, will be taken into consideration. The participant can only be randomized once the investigator receives the results and confirms the eligibility criteria.

*** Contact 1 (Day 2) will only be applicable for the sentinel participants in Phase 1. Remaining Phase 1 participants will not have a visit or contact at Day 2.

‡ Visit 4 and 5 will be replaced by a Contact if participant has received the standard of care vaccination against seasonal flu after Day 29 and prior to this visit and did not report any adverse events that would require physical examination on site.

Table 10 Intervals between study visits. Phase 2

Interval*	Planned visit interval	Allowed interval range
Visit 1 → Visit 2**	1 day	1 day
Visit 1 → Contact 1***	1 day	1 day
Visit 1 → Contact 2	2 days	2-3 days
Visit 1 → Visit 3†	7 days	6-8 days
Visit 1 → Visit 4	28 days	28-35 days
Visit 1 → Visit 5‡	91 days	84-98 days
Visit 1 → Visit 6‡	182 days	180-210 days

* Interval is computed as the difference between 2 dates

** Visit 2 (Day 2) will only be applicable for participants in the CCI [REDACTED] subset in Phase 2.

Remaining Phase 2 participants will not have a visit at Day 2.

*** Contact 1 (Day 2) will only be applicable for the sentinel OA participants in Phase 2. Remaining Phase 2 participants will not have a contact at Day 2.

† Visit 3 (Day 8) will be replaced by a Contact for all non-subset participants in Phase 2 and if participant did not report any adverse events that would require physical examination on site.

‡ Visit 5 and 6 will be replaced by a Contact if participant has received the standard of care vaccination against seasonal flu after Day 29 and prior to this visit and did not report any adverse events that would require physical examination on site.

6.1.5. Prior and Concomitant Medications

Concomitant medications are defined as any medications and vaccines (other than study intervention) taken after the study intervention administration. Any medication or vaccine (other than study intervention) started prior to the study intervention administration and continued after the study intervention administration will be considered a concomitant medication.

Concomitant medications/vaccinations will be coded using both the GSK Drug and WHO Drug dictionaries and will be listed and summarized descriptively (any medication, any antipyretic, and any antipyretic taken prophylactically, respectively) by study group using the ES.

The antipyretic classification is derived from the following ATC code:

ATC Code
A03D, A03DA, A03DB, A03DC, A03EA
M01, M01A, M01AA, M01AC, M01AE, M01AG, M01AB, M01AH, M01AX, M03B, M03BA, M03BB, M03BB, M03BC, M03BX
N02BG, N02AC, N02AG, N02AX, N02B, N02BA, N02BB, N02BE
R05, R05D, R05X

The percentage of participants using concomitant medication (any medication, any antipyretic and any antipyretic taken prophylactically, respectively) during the 28-day follow up period (i.e., Day 1 - Day 28 post-dosing) will be summarized by group.

This antipyretic list may be revised based on WHO dictionary version.

6.2. Appendix 2: Data Derivations Rule

6.2.1. Data derivation

6.2.1.1. Weight

Weight will be presented in kilograms. Weights reported in pounds will be converted as follows:

$$\text{Weight in kilograms} = \text{Weight in pounds} / 2.2$$

6.2.1.2. Height

Height will be presented in centimeters. Heights reported in feet and inches will be converted as follows:

$$\text{Height in centimeters} = \text{Height in inches} \times 2.54$$

6.2.1.3. Body Mass Index (BMI)

BMI will be calculated as follows:

$$\text{BMI} = (\text{Weight in kilograms}) / (\text{Height in meters})^2$$

6.2.1.4. Temperature

Temperatures will be presented in degrees Celsius (°C). Temperatures reported in degrees Fahrenheit (°F) will be converted as follows:

$$\text{Temperature (Celsius)} = ((\text{Temperature (Fahrenheit)} - 32) \times 5)/9$$

6.2.1.5. Numerical serology results

Numerical serology results will be derived from the content of IS.ISORRES in the SDTM dataset. For assays with a specific cut-off, with the exclusion of **CCI** data, the following derivation rules apply:

IS.ISORRES	Derived value
“NEG”, “-“, or “(-)”	cut-off/2
“POS”, “+”, or “(+)”	cut-off
“< value” and value is <= assay cut-off	cut-off/2
“< value” and value is > assay cut-off	value
“> value” and value is < assay cut-off	cut-off/2
“> value” and value is >= assay cut-off	value
“value” and value is < cut-off	cut-off/2
“value” and value is >= cut-off	value
All other cases	missing

6.2.1.6. Geometric Mean Titres (GMTs) and Concentrations (GMCs)

Geometric Mean Titre (GMT) or Concentration (GMC) calculations are performed by taking the inverse logarithm of the mean of the log titre or concentration transformations. Non quantifiable titres or concentrations will be converted as described in Section 6.2.1.5 for the purpose of GMT/GMC calculation. Cut-off values are defined by the laboratory before the analysis.

6.2.1.7. Onset Day

The onset day for an event (e.g., AE, concomitant medication/vaccination) is the number of days between the study dose administration and the start date of the event. This is 1 for an event occurring on the same day as a study dose (and reported as starting after study dose).

6.2.1.8. Study Day

Study day will be calculated as follows:

- Study day prior to dosing will be calculated as: date of assessment – date of the study intervention administration
- Study day on or after the date of the dosing will be calculated as: date of assessment – date of the study intervention administration + 1.

6.2.1.9. Duration of Events

The duration of an event with a start and end date will be the difference between the start and end date plus 1 day, i.e., an event that starts on 03MAR2018 and ends on 12MAR2018 has a duration of 10 days.

For any grade, duration of solicited AE is defined as Start date – Stop date + 1, with Start date defined as the first day with the symptom at Grade ≥ 0 within the 7-day solicitation period and Stop date defined as the last day with the symptom (i.e., Grade > 0) in or beyond the solicited period. For solicited AE continuing beyond Day 28, stop date will be assigned the end of study.

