The duration of solicited AEs of any grade (see Section 6.2.1.9) will be summarized. The start date is the first day during the 7-day solicitation period with the symptom at grade > 0 while the stop date is the last day with the symptom at grade > 0 in or beyond the solicited period. In addition, the duration for specific grade(s) for each symptom defined as the number of days in the reporting period with grade above or equal to specific grade will be summarized.

Prolonged solicited AEs that continue beyond Day 7 or Day 28 will be identified using a flag in listing of AEs.

The number of completed eDiary days in the solicited period for a participant will be summarized by study group using frequency table.

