6.2.2.3. Daily Recording of Solicited Events

For studies **using electronic diaries** for the collection of solicited events, a solicited event will be considered present only when a daily recording of Grade 1 or more is present. To determine the grading, the following rule will be used:

Administration Site (Local) reaction	Mild (Grade 1)	Moderate (Grade 2)	Severe (Grade 3)
Pain	Mild: Any pain neither interfering with nor preventing normal everyday activities.	Moderate: Painful when limb is moved and interferes with everyday activities.	Significant pain at rest. Prevents normal everyday activities.
Redness *	25 – 50 mm	51 – 100 mm	>100 mm
Swelling **	25 – 50 mm	51 – 100 mm	> 100 mm
Lymphadenopathy***	Present but does not interfere with activity	Interferes with normal activity	Prevents normal activity

* For redness and swelling, in addition to grading the measured administration site reaction at the greatest single diameter, the measurement should be recorded as a continuous variable.

** Swelling should be evaluated and graded using the functional scale as well as the actual measurement.

*** Defined as localized axillary, cervical or supraclavicular swelling or tenderness ipsilateral to the administration arm.

Systemic (General)	Mild (Grade 1)	Moderate (Grade 2)	Severe (Grade 3)
Fever (°C) * (°F) *	38.0 – 38.4 100.4 – 101.1	38.5 – 38.9 101.2 – 102.0	>38.9 >102.0
Headache	Headache that is easily tolerated	Headache that interferes with normal activity	Headache that prevents normal activity
Fatigue	Fatigue that is easily tolerated	Fatigue that interferes with normal activity	Fatigue that prevents normal activity
Myalgia	Myalgia present but does not interfere with activity	Myalgia that interferes with normal activity	Myalgia that prevents normal activity
Arthralgia	Arthralgia present but does not interfere with activity	Arthralgia that interferes with normal activity	Arthralgia that prevents normal activity
Chills	Chills present but do not interfere with activity	Chills that interfere with normal activity	Severe: chills that prevent normal activity

* Axillary temperature.

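### SAP 6.2.1.9 reverses the subtraction and starts the clock at Grade ≥ 0, so its solicited-event duration rule contradicts the rest of the SAP

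*SAP*

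**What the plan says.** SAP 4.2.1.1 announces the summary and names the section that governs it: "The duration of solicited AEs of any grade (see Section 6.2.1.9) will be summarized". It then states when an event begins: "The start date is the first day during the 7-day solicitation period with the symptom at grade > 0". It puts the end on the last day above grade 0, and it gives no formula.

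SAP 6.2.1.9 has two paragraphs. The first is a general rule, under which duration "will be the difference between the start and end date plus 1 day", with the illustration that "an event that starts on 03MAR2018 and ends on 12MAR2018 has a duration of 10 days". The second is specific to solicited events of any grade. Its formula reads: "duration of solicited AE is defined as Start date – Stop date + 1". The beginning of the interval is fixed by the next clause of that sentence: "with Start date defined as the first day with the symptom at Grade ≥ 0 within the 7-day solicitation period". The end of the event is given as "Stop date defined as the last day with the symptom (i.e., Grade > 0) in or beyond the solicited period".

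SAP 6.2.2.3 fixes when an event exists at all: "a solicited event will be considered present only when a daily recording of Grade 1 or more is present".

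Two further facts bear on how the rule works. Grade 0 is a defined grade in protocol Table 26 (section 10.3.5.3): no symptom for headache and similar events, under 25 mm for redness and swelling, under 38.0°C for temperature. SAP 4.2.1.1 also requires diary recording on Days 1 to 7 whether or not an event occurs.

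**The concern.** The sentence a programmer is sent to for this derivation contains two separate errors.

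- **Order of subtraction.** Start minus stop plus 1 cannot give a positive number for any event longer than one day.
- **Threshold.** The grade scale begins at 0, so Grade ≥ 0 is met by every completed diary day, including a symptom-free one. Read literally, the start date is the first completed diary day, normally Day 1, whatever the true onset. The stop date in the same sentence uses Grade > 0, so the two ends of the interval follow different thresholds.

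At stake is whether the reported durations of solicited events describe the symptoms. The two errors differ in how easily they would be noticed. Negative durations would stand out in the first output. A start date set too early would not, because once the sign is corrected every duration is positive and believable.

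**Working it through.** **Inputs.** Start rule, stop rule, formula and worked example: SAP 6.2.1.9. Competing start rule: SAP 4.2.1.1. Presence rule: SAP 6.2.2.3. Meaning of Grade 0: protocol Table 26. Assumption: a diary entry exists for Day 1.

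**Step 1: the SAP's own figure.** For 3 to 12 March, end − start + 1 = 12 − 3 + 1 = 10 days, as stated. The solicited-event formula on the same dates, even with the correct start day, gives 3 − 12 + 1 = −8.

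**Step 2: general form.** Let a be the true onset day (1 to 7) and b the last symptomatic day.

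- Intended: b − a + 1.
- As printed (start falls on Day 1, subtraction reversed): 1 − b + 1 = 2 − b.
- Subtraction corrected, Grade ≥ 0 kept: b − 1 + 1 = b. The excess is b − (b − a + 1) = a − 1, at most 7 − 1 = 6 days.
- Threshold corrected, subtraction still reversed: a − b + 1. This is right only for one-day events, zero for two-day events and negative for longer ones.

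**Step 3: examples (days).**

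| Event (onset to last day) | Intended | As printed | Subtraction fixed only | Threshold fixed only |
|---|---|---|---|---|
| Day 1 to 1 | 1 | 1 | 1 | 1 |
| Day 1 to 2 | 2 | 0 | 2 | 0 |
| Day 2 to 2 | 1 | 0 | 2 | 1 |
| Day 3 to 5 | 3 | −3 | 5 | −1 |
| Day 4 to 6 | 3 | −4 | 6 | −1 |
| Day 5 to 7 | 3 | −5 | 7 | −1 |
| Day 6 to 10 | 5 | −8 | 10 | −3 |

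**Step 4: all combinations.** With onset on Day 1 to 7 and the last day anywhere from onset to Day 28, there are 28 + 27 + 26 + 25 + 24 + 23 + 22 = 175 pairs. The printed rule gives 172 negative values, 2 zeros (Day 1 to 2 and Day 2 to 2) and 1 correct value (Day 1 to 1). Correcting only the subtraction gives the right answer in the 28 pairs with onset on Day 1. Correcting only the threshold gives it in the 7 one-day pairs. Both edits are needed. These counts are of possible day pairs, not of expected participants.

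Events continuing past Day 28 fall under a separate stop-date sentence in the same section and are not part of this check.

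**The case against.** The best defence is that the intended rule is not in doubt. SAP 4.2.1.1 has the right threshold at both ends. The general rule and example in 6.2.1.9 have the right order of subtraction. The disputed sentence speaks of a day with the symptom, and a few words later explains that phrase as Grade > 0; a symptom-free day is not naturally a day with the symptom. A programmer who met negative durations would look again and probably find the right rule.

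Much of this stands, and it makes the point a contradiction in drafting rather than proof that the reported durations will be wrong. It does not clear the sentence. Section 4.2.1.1 contains no formula and sends the reader to 6.2.1.9, and nothing says which section prevails. The wording also does not fully rescue the threshold. A redness of, say, 10 mm is a visible reaction at Grade 0, and SAP 6.2.2.3 asks for redness and swelling to be recorded as continuous measurements, so such values can be in the data.

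A reader might also infer that a co-primary endpoint is damaged, or that the comparison of mRNA vaccine with control is distorted. The documents support neither. The co-primary solicited endpoint in protocol Table 5 and SAP Table 1 is occurrence, as a percentage of participants. Protocol 9.3.1 lists no duration analysis. SAP Table 2 states that no treatment comparison is planned for the safety and reactogenicity objective, and nothing in the documents shows that onset timing differs between groups.

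**Conclusion.** The point holds as an internal contradiction in an operative derivation rule. Followed literally, the rule fails for every event except a one-day event on Day 1. If it is half corrected, each duration is overstated by the onset day minus 1, from 0 to 6 days. The overstatement is not a consequence of the rule as printed, which yields negative numbers; it arises only when the subtraction is repaired and Grade ≥ 0 is left in place. That half correction deserves attention because its output looks normal.

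The size rests on a completed Day 1 diary entry. If the first entry is later, the false start date moves to that day and the overstatement shrinks accordingly.

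The reach is narrow: the descriptive any-grade duration summary. The occurrence percentages, the separate count of days at or above a given grade, the Bayesian logistic regression model, the holding rules and the sample size do not use this formula. The sentence should be corrected before the duration tables are programmed, but no conclusion about safety or dose selection depends on it.

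**What to change.** Make two edits to the solicited-event sentence in SAP 6.2.1.9:

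1. Define duration as Stop date – Start date + 1.
2. Define the start date as the first of Days 1 to 7 on which the symptom is recorded at Grade > 0.

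Leave the stop-date definition in that sentence unchanged. The rule then agrees with 4.2.1.1 and 6.2.2.3. Applied to the dates of the worked example it gives 10 days, and an event on Days 4 to 6 gives 6 − 4 + 1 = 3.

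The cost is one corrected sentence. No new data, analysis or change to the protocol is needed, and there is no analytical downside. If duration programs already exist, check them for both errors, since correcting the sign alone would leave the threshold error in place.
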